### 8.8.4 Sensitivity Analysis of Site 1156

To assess the impact of site 1156 on key endpoints the below analyses will be conducted utilising the modified populations (see section 6.0) which removes subjects enrolled from site 1156:

- Analysis of Proportion of Subject Achieving Normalisation of Total Testosterone (300-1000 ng/dl). Analysis will be conducted on the Central lab testosterone using LOCF imputation.
- Summary of Change in LH and FSH
- Summary of Vitals signs Parameters and Change from Baseline
- Summary of Blood Pressure Categorisation
- Summary of Body Composition

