#### 6.1.1 Modified Intention-To-Treat Population (MITT)

The mITT population includes all subjects who are included in the ITT but were not enrolled from site 1156

Subjects will be analysed according to the treatment to which they were randomised.

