#### 6.2.1 Modified Safety Population (MSafety)

The modified safety population includes all subjects who are included in the Safety Population but were not enrolled from site 1156.

Subjects will be analysed according to the treatment actually received. Subjects who did not receive the treatment planned by the randomisation will be analysed according to the treatment received.

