#### 8.1.1 Populations for analysis

Demographic and baseline characteristics will be summarised by Safety, Completers and ITT populations, unless otherwise stated.

Analyses of the primary endpoint and secondary safety BMD endpoints will be performed on ITT and completer population. Analysis of all other safety endpoints will use the safety population.

The secondary efficacy endpoints and exploratory endpoints will be analysed using the ITT population.

The safety and tolerability variables will be analysed using the Safety population.

PK data will be analysed using the PK population.

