### 8.1.7 Data listings

All relevant subject data collected during the MBGS206 study, including those derived will be presented in individual subject data listings. Selected data from study MBGS205 will also be presented to aid in interpretation (e.g MBGS205 baseline) All listings will be sorted by treatment regimen, investigational site, subject number, date/time and visit. The subject's age will be stated on each listing. Unless otherwise stated, data listings will be based on all subjects randomised.

Unscheduled visit results will be included in date/time chronological order within subject listings, but will not be tabulated.

---

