#### 8.6.2 Analysis of primary endpoint

The Primary Endpoint is defined as the change in lumbar bone density measured by DEXA from baseline in Study MBGS205 to Week 48 in Study MBGS206 by dose group in subjects randomised to active treatment in Study MBGS205.

DXA Scan assessments will only be performed at the EOT visit (for subjects that reached at least Week 36) and will be over-read by IMI. The DEXA over-read data will be used for the primary endpoint statistical analysis.

Descriptive statistics (observed values, changes from baseline and percentage change from baseline) in lumbar bone mineral density will be presented for each treatment regimen and time-point. A single sample 1-sided t-test conducted at the 2.5% significance level will be used to analyse percentage change from Baseline (MBGS205) to Week 48 (MBGS206) LOCF in each treatment arm to test the null hypothesis that the percentage decrease from Baseline is  $\leq 3\%$ . P-values and associated CI will be presented.

Only subjects included in the safety population that have a post-Baseline DEXA assessment in MBGS206 and were randomised to active treatment in Study MBGS205 will be included in this analysis. The analysis will be repeated for subjects included in the completer population.

Observed and percentage change from baseline values at each visit will be presented in a line graph by treatment group.

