### 9 CHANGES TO PLANNED ANALYSIS FROM STUDY PROTOCOL

The below are changes to the study protocol analysis:

The Percentage change in lumbar bone mineral density measured by DEXA (g/cm^2) from Baseline in Study MBGS206 to Week 48 for subjects that were randomised to placebo in Study MBGS205 has been added as a secondary safety endpoint. This was inadvertently absent from the study protocol.

Vitamin D deficiency is defined in the protocol as <20ng/ml. For all analyses Vitamin D deficiency has been defined as <30ng/ml.

Following data integrity concerns at site 1156, sensitivity analyses were added to assess the impact of the site on key parameters.

---

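### The analyses that leave out site 1156, where data integrity is in doubt, omit the primary endpoint: every planned lumbar and hip BMD analysis keeps the site

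*SAP*

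**What the plan says.** SAP section 9 gives the reason for the extra analyses: "Following data integrity concerns at site 1156, sensitivity analyses were added to assess the impact of the site on key parameters". Two populations are built for them. Section 6.1.1: "The mITT population includes all subjects who are included in the ITT but were not enrolled from site 1156". Section 6.2.1: "The modified safety population includes all subjects who are included in the Safety Population but were not enrolled from site 1156".

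Section 8.8.4 then states the purpose, "To assess the impact of site 1156 on key endpoints the below analyses will be conducted utilising the modified populations", and lists five items:

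- testosterone normalisation (central laboratory values, LOCF)
- change in LH and FSH
- vital signs
- blood-pressure categories
- body composition

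For BMD, section 8.1.1 says: "Analyses of the primary endpoint and secondary safety BMD endpoints will be performed on ITT and completer population". Section 8.6.2 describes the primary test differently, starting with: "Only subjects included in the safety population that have a post-Baseline DEXA assessment in MBGS206". It adds a repeat in completers. Section 8.7, which contains the hip BMD and T-score analyses, uses the Safety population.

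**The concern.** The trial exists to answer a bone-safety question, and lumbar BMD is the only endpoint with a sample-size calculation. The sponsor doubted one site's data enough to define two populations without it and to re-run what it calls key endpoints. The endpoint that carries the trial's conclusion is not among them.

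As planned, the report could show that testosterone and blood pressure hold up without the site, but not whether the BMD result does. With about 25 men per dose, a few men from one site can move an arm mean. A reader who asks about this would have to rebuild each arm's estimate and interval from listings.

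**Working it through.** **Step 1. Compare the list with the BMD analyses.**

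| BMD analysis | SAP section | Population | Site 1156 |
|---|---|---|---|
| Primary and secondary BMD endpoints | 8.1.1 | ITT and completers | kept |
| Primary lumbar test | 8.6.2 | Safety with a post-baseline DEXA | kept |
| Repeat of the primary test | 8.6.2 | Completers, drawn from Safety (6.3) | kept |
| Hip BMD, T-scores, MMRM, ANCOVA, vitamin D subgroups | 8.7 and 8.7.1 | Safety | kept |

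- Body composition does not bring BMD in by another name. Section 8.6.4.1 defines it through weight, BMI, waist and hip measurements, gynecomastia and bio-impedance, with no DEXA.
- Result: 0 of the 5 site-excluded analyses concern BMD, and 0 of the planned BMD analyses exclude the site. This holds whichever of sections 8.1.1 and 8.6.2 governs the primary analysis.
- Nothing else fills the gap. Section 8.6.1.2 rules out a treatment-by-centre analysis. Section 6.6 provides for documented exclusions but names none for this site, and the modified sets only make sense if the site remains in the parent sets. No completer set without the site is defined.
- SAP section 6.1 admits a subject to ITT only if he has a lumbar spine value at baseline and at least one after baseline in MBGS206. The mITT set is therefore already the set of men outside site 1156 with evaluable lumbar BMD. It is available to the plan but not used for that endpoint.

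**Step 2. Reproduce the plan's own figure.** The protocol synopsis has 30 men entering per previously active arm, about 17% dropout and about 25 completers: 30 × (1 − 0.17) = 24.9, which agrees. The 90% power statement cannot be fully reproduced because the detectable decrease is redacted. For a one-sample t-test at two-sided 5% with n = 25, 90% power corresponds to a difference of 0.676 SD. With the protocol section 13.1 SD of 0.0439 g/cm², that is 0.676 × 0.0439 = 0.0297 g/cm².

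**Step 3. How far could the site move an arm mean?** The documents do not give the site's size or the direction of any error, so *k* and *s* are assumptions. If *k* of 25 men differ by *s* percentage points from the rest, the arm mean shifts by *k* × *s* / 25, in either direction.

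| | s = 1 | s = 3 | s = 5 |
|---|---|---|---|
| k = 1 | 0.04 | 0.12 | 0.20 |
| k = 3 | 0.12 | 0.36 | 0.60 |
| k = 5 | 0.20 | 0.60 | 1.00 |

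**Step 4. What precision would the sensitivity analysis lose?** The 95% CI half-width is t(0.975, n − 1) × SD / √n. Power is for the 0.676 SD difference of Step 2.

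| Men removed | n | Half-width (SD units) | Ratio to n = 25 | Power |
|---|---|---|---|---|
| 0 | 25 | 0.413 | 1.00 | 90% |
| 1 | 24 | 0.422 | 1.02 | 88.7% |
| 3 | 22 | 0.443 | 1.07 | 85.6% |
| 5 | 20 | 0.468 | 1.13 | 81.8% |

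The ratios do not depend on the SD. To express the half-widths in percentage points, two assumptions are needed: a baseline BMD of 1.0–1.2 g/cm² (not given), and that 0.0439 is the SD of the change (the protocol does not say). The SD is then 0.0439/1.0 = 4.39% to 0.0439/1.2 = 3.66%. The half-width is 1.81–1.51 points at n = 25, 1.95–1.62 at n = 22 and 2.05–1.71 at n = 20.

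**The case against.** The strongest reply is that the consequence is unproven. The sponsor knew what had gone wrong at the site and chose a targeted list, so leaving out BMD may have been deliberate. Several features of the plan and design support this view.

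- **Central reading.** "The DEXA over-read data will be used for the primary endpoint statistical analysis", and section 8.7.1 also analyses the site's own readings, so reading errors at the site have a check.
- **Listings.** "All listings will be sorted by treatment regimen, investigational site, subject number, date/time and visit", so the site's BMD values can be inspected.
- **Site size.** The protocol synopsis expects about 50 sites. Three active arms of about 25 completers give 75/50 = 1.5 men per site, or 0.5 per arm. Three to five men in one arm would be 6 to 10 times the average.
- **Yardstick.** A shift should be judged against the CI as well as the 3% threshold. The 0.36-point case is about 20–24% of the 1.51–1.81-point half-width, and one man moves the mean by at most about 13% of it (0.20/1.51).
- **Status.** All analyses are declared exploratory.

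Part of this stands. No bias in the BMD result can be shown from the documents, and the upper end of the illustration needs a large site and a large deviation together. The rest does not remove the gap. Central measurement was not the plan's reason for exemption, since section 8.8.4 re-runs central-laboratory testosterone. Over-read and dual readings test how a scan was read, not how it was acquired or whether the eligibility, dosing and other subject data are sound. Listings are not an analysis. The five listed items are equally exploratory, and the primary endpoint still has a formal one-sided test against 3%. If the site is small, the added table would show that.

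**Conclusion.** The concern holds. That BMD is missing from the site-excluded analyses is certain from the text and rests on no assumption.

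Its effect on the result is unknown. Under the assumed range of one to five men per arm and a 1–5 point difference, the mean would shift by 0.04 to 1.0 points, with the lower part more plausible for a site of average size. The nature of the concern is not stated, so its relevance to BMD can be neither assumed nor excluded.

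The primary analysis is not invalid. The plan should be corrected because the report could not otherwise show whether its main conclusion depends on a site whose data are in question.

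**What to change.** Add to SAP section 8.8.4:

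1. The primary lumbar BMD percentage change per dose (estimate, 95% CI and the one-sided t-test) and the hip BMD summaries, on the modified safety set with a post-baseline DEXA and on mITT. These should be nearly the same men, so one table will do if they coincide.
2. A statement of which primary set is being mirrored, because sections 8.1.1 and 8.6.2 differ. If the completer repeat is mirrored too, it needs a completer flag without the site.
3. The number of site 1156 subjects in each arm.

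State in advance that the results will be read by comparing estimates and CIs with and without the site. The same test outcome should not be required, since the smaller n alone can change it. Re-runs of bone markers, T-scores, testosterone overshoot and adverse events of special interest are optional.

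The cost is a few more tables from existing programs on largely existing population flags. No new data are needed. The sensitivity-analysis CIs would be slightly wider, up to about 13% if five men per arm were removed.

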### 8.9 CSR

The primary efficacy analysis will be performed when all data has been collected.

---

### 9 CHANGES TO PLANNED ANALYSIS FROM STUDY PROTOCOL

The below are changes to the study protocol analysis:

The Percentage change in lumbar bone mineral density measured by DEXA (g/cm^2) from Baseline in Study MBGS206 to Week 48 for subjects that were randomised to placebo in Study MBGS205 has been added as a secondary safety endpoint. This was inadvertently absent from the study protocol.

Vitamin D deficiency is defined in the protocol as <20ng/ml. For all analyses Vitamin D deficiency has been defined as <30ng/ml.

Following data integrity concerns at site 1156, sensitivity analyses were added to assess the impact of the site on key parameters.

---

## 11 APPENDICES

### **Appendix A - International Index of Erectile Function (IIEF)**

Question Number	Question	Response	Score
1	Over the past 4 weeks how often were you able to get an erection during sexual activity?	Almost always or always	5
		Most times (much more than half the time)	4
		Sometimes (about half the time)	3
		A few times (much less than half the time)	2
		Almost never or never	1
		No sexual activity	0
2	Over the past 4 weeks when you had erections with sexual stimulation, how often were your erections hard enough for penetration?	Almost always or always	5
		Most times (much more than half the time)	4
		Sometimes (about half the time)	3
		A few times (much less than half the time)	2
		Almost never or never	1
		No sexual stimulation	0
3	Over the past 4 weeks when you attempted sexual intercourse how often were you able to penetrate (enter) your partner?	Almost always or always	5
		Most times (much more than half the time)	4
		Sometimes (about half the time)	3
		A few times (much less than half the time)	2
		Almost never or never	1
		Did not attempt intercourse	0
4	Over the past 4 weeks during sexual intercourse how often were you able to maintain your erection after you had penetrated (entered) your partner?	Almost always or always	5
		Most times (much more than half the time)	4
		Sometimes (about half the time)	3
		A few times (much less than half the time)	2
		Almost never or never	1
		Did not attempt intercourse	0
5	Over the past 4 weeks during sexual intercourse how difficult was it to maintain your erection to completion of intercourse?	Not difficult	5
		Slightly difficult	4
		Difficult	3
		Very difficult	2
		Extremely difficult	1
		Did not attempt intercourse	0
6	Over the past 4 weeks how many times have you attempted sexual intercourse?	11+ attempts	5
		7-10 attempts	4
		5-6 attempts	3
		3-4 attempts	2
		1-2 attempts	1
		No attempts	0
7	Over the past 4 weeks when you attempted sexual intercourse how often was it satisfactory for you?	Almost always or always	5
		Most times (much more than half the time)	4
		Sometimes (about half the time)	3
		A few times (much less than half the time)	2
		Almost never or never	1

		Did not attempt intercourse	0
8	Over the past 4 weeks how much have you enjoyed sexual intercourse?	Very highly enjoyable	5
		Highly enjoyable	4
		Fairly enjoyable	3
		Not very enjoyable	2
		Not enjoyable	1
		No intercourse	0
9	Over the past 4 weeks when you had sexual stimulation or intercourse how often did you ejaculate?	Almost always or always	5
		Most times (much more than half the time)	4
		Sometimes (about half the time)	3
		A few times (much less than half the time)	2
		Almost never or never	1
		No sexual stimulation or intercourse	0
10	Over the past 4 weeks when you had sexual stimulation or intercourse how often did you have the feeling of orgasm with or without ejaculation?	Almost always or always	5
		Most times (much more than half the time)	4
		Sometimes (about half the time)	3
		A few times (much less than half the time)	2
		Almost never or never	1
		No sexual stimulation or intercourse	0
11	Over the past 4 weeks how often have you felt sexual desire?	Almost always or always	5
		Most times (much more than half the time)	4
		Sometimes (about half the time)	3
		A few times (much less than half the time)	2
		Almost never or never	1
12	Over the past 4 weeks how would you rate your level of sexual desire?	Very high	5
		High	4
		Moderate	3
		Low	2
		Very low or none at all	1
13	Over the past 4 weeks how satisfied have you been with your overall sex life?	Very satisfied	5
		Moderately satisfied	4
		About equally satisfied and dissatisfied	3
		Moderately dissatisfied	2
		Very dissatisfied	1
14	Over the past 4 weeks how satisfied have you been with your sexual relationship with your partner?	Very satisfied	5
		Moderately satisfied	4
		About equally satisfied and dissatisfied	3
		Moderately dissatisfied	2
		Very dissatisfied	1
15	Over the past 4 weeks how would you rate your confidence that you could get and keep an erection?	Very high	5
		High	4
		Moderate	3
		Low	2
		Very	1

**Appendix B - Patient-Reported Outcomes Measurement Information System(®)  
Sexual Function and Satisfaction (PROMIS(®) SexFS)**

Question Number	Question	Response	Score
1	How interested have you been in sexual activity?	Very	5
		Quite a bit	4
		Somewhat	3
		A little bit	2
		Not at all	1
2	How often have you felt like you wanted to have sexual activity?	Always	5
		Often	4
		Sometimes	3
		Rarely	2
		Never	1
3	Please rate your ability to have an erection.	Very good	5
		Good	4
		Fair	3
		Poor	2
		Very Poor	1
4	How satisfied have you been with your sex life?	Very	5
		Quite a bit	4
		Somewhat	3
		A little bit	2
		Not at all	1
5	How much pleasure has your sex life given you?	A lot	5
		Quite a bit	4
		Somewhat	3
		A little bit	2
		None	1
6	How often have you thought that your sex life is wonderful?	Always	5
		Often	4
		Sometimes	3
		Rarely	2
		Never	1
7	How satisfied have you been with your sexual relationship(s)?	Very	5
		Quite a bit	4
		Somewhat	3
		A little bit	2
		Not at all	1
		Have not had a sexual relationship in last 30 days	0
8	When you have had sexual activity, how much have you enjoyed it?	Very much	5
		Quite a bit	4
		Somewhat	3
		A little bit	2
		Not at all	1
9	How much has fatigue or lack of energy affected your	Very Much	5
		Quite a bit	4

	satisfaction with your sex life?	Somewhat	3
		A little bit	2
		Not at all	1
		Have not had fatigue or lack of energy in the last 30 days	0
10	How much has weight gain affected your satisfaction with your sex life?	Very Much	5
		Quite a bit	4
		Somewhat	3
		A little bit	2
		Not at all	1
		Have not had weight gain in the last 30 days	0

### T-Score Conversion Tables :

1. Interest in Sexual Activity (1,2)

Q1 Raw	Q2 Raw	T Score
1	1	33.4
1	2	40.1
1	3	44.5
1	4	50.3
1	5	55.3
2	1	39.8
2	2	43.6
2	3	47.6
2	4	52.7
2	5	57.4
3	1	43.1
3	2	46.7
3	3	51.1
3	4	55.5
3	5	60.1
4	1	45.4
4	2	49.3
4	3	54.5
4	4	59
4	5	63.8
5	1	47.1
5	2	51.2
5	3	57.5
5	4	63.2
5	5	70

2. Erectile Function (3)

Q3 Raw	T score
1	31.4
2	36.6
3	40.4
4	45.6
5	56.3

3. Satisfaction with Sex Life (4,5,6,7,8)

Satisfaction with Sex  
Life Tscore.xlsx

**Appendix C - PROMIS(®) Fatigue Short Form**

Question Number	Question	Response	Score
1	I feel fatigued	Very much	5
		Quite a bit	4
		Somewhat	3
		A little bit	2
		Not at all	1
2	I have trouble starting things because I am tired	Very much	5
		Quite a bit	4
		Somewhat	3
		A little bit	2
		Not at all	1
3	How run-down did you feel on average?	Very much	5
		Quite a bit	4
		Somewhat	3
		A little bit	2
		Not at all	1
4	How fatigued were you on average?	Very much	5
		Quite a bit	4
		Somewhat	3
		A little bit	2
		Not at all	1
5	How much were you bothered by your fatigue on average?	Very much	5
		Quite a bit	4
		Somewhat	3
		A little bit	2
		Not at all	1
6	To what degree did your fatigue interfere with your physical functioning?	Very much	5
		Quite a bit	4
		Somewhat	3
		A little bit	2
		Not at all	1
7	How often did you have to push yourself to get things done because of your fatigue?	Always	5
		Often	4
		Sometimes	3
		Rarely	2
		Never	1
8	How often did you have trouble finishing things because of your fatigue?	Always	5
		Often	4
		Sometimes	3
		Rarely	2
		Never	1

T-Score Conversion Table:

Fatigue 8a		
Short Form Conversion Table		
Raw Score	T-score	SE*
8	33.1	4.8
9	38.5	2.7
10	41.0	2.2
11	42.8	2.0
12	44.3	1.9
13	45.6	1.8
14	46.9	1.8
15	48.1	1.8
16	49.2	1.8
17	50.4	1.8
18	51.5	1.7
19	52.5	1.7
20	53.6	1.7
21	54.6	1.7
22	55.6	1.7
23	56.6	1.7
24	57.5	1.7
25	58.5	1.7
26	59.4	1.7
27	60.4	1.7
28	61.3	1.7
29	62.3	1.7
30	63.3	1.7
31	64.3	1.7
32	65.3	1.7
33	66.4	1.7
34	67.5	1.7
35	68.6	1.7
36	69.8	1.8
37	71.0	1.8
38	72.4	2.0
39	74.2	2.4
40	77.8	3.7

\*SE = Standard Error

Reference : <https://www.assessmentcenter.net/>

### Appendix D - 36-Item Short Form Health Survey (SF-36)

VARIABLE	DERIVATION
SF-36 PF scale score	
raw score = sum (items 3A, 3B, 3C, 3D, 3E, 3F, 3G, 3H, 3I, 3J)
 
<math>PF = (\text{raw score} - 10) * 5</math>
 
<math>PF\_Z = (PF - 82.62455) / 24.43176</math>
 
PF scale score = (PF_Z*10) + 50
 
When calculating the raw score, if 5 or more of the items are non-missing then replace any missing values as follows:
 
Calculate the mean of the answered questions, using the number of answered questions as the denominator. Substitute the mean for any missing scores.
 
Otherwise, if less than 5 of the items are non-missing then PF scale score is missing.
 
The response scale for each activity ranges from 1 to 3 where 1=limited a lot, 2=limited a little, and 3=not limited at all.
 
A higher PF scale score indicates better physical functioning.

SF-36 RP scale score	
raw score = sum (items 4A, 4B, 4C, and 4D )
 
<math>RP = [(\text{raw score} - 4) / 16] * 100</math>
 
<math>RP\_Z = (RP - 82.65109) / 26.19282</math>
 
RP scale score = (RP_Z * 10) + 50
 
When calculating the raw score, if 2 or more of the items are non-missing then replace any missing values as follows:
 
Calculate the mean of the answered questions, using the number of answered questions as the denominator. Substitute the mean for any missing scores.
 
Otherwise, if less than 2 of the items are non-missing then RP scale score is missing.
 
The response scale for each item ranges from 1 to 5 where 1=All of the time, 2=Most of the time, 3=Some of the time, 4=A little of the time, and 5=None of the time.
 
A higher RP scale score indicates better role-physical functioning.


SF-36 BP scale score
	
raw score = sum (reversed item 7 and reversed item 8)  <math>BP = (\text{raw score} - 2) * 10</math>  <math>BP\_Z = (BP - 73.86999) / 24.00884</math>  BP scale score = <math>(BP\_Z * 10) + 50</math>
 
Reverse direction of Item 7 as follows: if =1, set to 6; if =2, set to 5.4; if =3, set to 4.2; if =4, set to 3.1; if =5, set to 2.2 if =6, set to 1.
 
Reverse direction of item 8 as follows:  if =1 and original value of item 7 =1, set to 6;  if =1 and original value of item 7 >=2, set to 5; if =2, set to 4;  if =3, set to 3; if =4, set to 2; if =5, set to 1.
 
If item 7 is answered and item 8 is missing, set 8 = reversed 7 as defined above. If 8 is answered and 7 is missing, set 7 as reverse item 8 as follows:  if =1, set to 6;  if =2, set to 4.75; if =3, set to 3.5; if =4, set to 2.25;  if =5, set to 1.
 
If 1 or more questions were answered, calculate BP scale score as defined above. If neither question was answered then BP scale score is missing.
 
The scale for Question 7, amount of bodily pain, ranges from 1 to 6 where 1=None, 2=Very mild, 3=mild, 4=Moderate, 5=Severe, and 6=Very severe. The scale for Question 8, the degree to which pain interfered with normal work, ranges from 1 to 5 where 1=Not at all, 2=A little bit, 3=Moderately, 4=Quite a bit, and 5=Extremely.
 
A higher BP scale score indicates lack of bodily pain.


SF-36 GH scale score
	
raw score = sum (reversed item 1, item 11A, reversed 11B, 11C and reversed 11D) <math>GH = (\text{raw score} - 5) * 5</math>  <math>GH\_Z = (GH - 70.78372) / 21.28902</math>  GH scale score = <math>(GH\_Z * 10) + 50</math>
 
Reverse direction of Item 1 as follows:  if =1, set to 5;  if =2, set to 4.4; if =3, set to 3.4; if =4, set to 2; if =5, set to 1.
 
Reverse direction of item 11B and 11D by subtracting score from 6.
 
When calculating the raw score, if 3 or more of the items are non-missing then replace any missing values as follows:
 
Calculate the mean of the answered questions, using the number of answered questions as the denominator. Substitute the mean for any missing scores.
 
Otherwise, if less than 3 of the items are non-missing then GH scale score is missing.
 
Responses for Question 1, an assessment of self-perceived health status, range from 1 to 5 where 1=Excellent, 2=Very good, 3=Good, 4=Fair, and 5=Poor. Responses for the items in Question 11 range from 1 to 5 where 1=Definitely true, 2=Mostly true, 3=Don't know, 4=Mostly false, and 5=Definitely false and reflect the subject's perception of their relative health and expectations of their future health status.
 
A higher GH scale score indicates better general health perceptions.

SF-36 VT scale score	
raw score = sum (reversed item 9a, reversed 9e, 9g and 9i)  <math>VT = [(raw\ score - 4) / 16] * 100</math>  <math>VT\_Z = (VT - 58.41968) / 20.87823</math>  <math>VT\ scale\ score = (VT\_Z * 10) + 50</math>
 
Reverse direction of Items 9a and 9e by subtracting score from 6.
 
When calculating the raw score, if 2 or more of the items are non-missing then replace any missing values as follows:
 
Calculate the mean of the answered questions, using the number of answered questions as the denominator. Substitute the mean for any missing scores.
 
Otherwise, if less than 2 of the items are non-missing then VT scale score is missing.
 
The scale for these items ranges from 1 to 5 where 1=All of the time, 2=Most of the time, 3=Some of the time, 4=A little of the time, and 5=None of the time.
 
A higher VT scale score indicates more vitality.

SF-36 SF scale score	
raw score = sum (reversed 6 and 10)  <math>SF = [(raw\ score - 2) / 8] * 100</math>  <math>SF\_Z = (SF - 85.11568) / 23.24464</math>  <math>SF\ scale\ score = (SF\_Z * 10) + 50</math>
 
Reverse direction of score for item 6 by subtracting score from 6.
 
When calculating the raw score, if 1 of the items is missing then substitute the missing score with the score on the non-missing item. If both items are missing then SF scale score is missing.
 
Responses to Question 6, an assessment of the extent to which health/emotional problems interfered with social activities, range from 1 to 5 where 1=Not at all, 2=Slightly, 3=Moderately, 4=Quite a bit, and 5=Extremely.
 
Responses to Question 10 reflect the amount of time that health/emotional problems interfered with social activities and range from 1 to 5 where 1=All of the time, 2=Most of the time, 3=Some of the time, 4=A little of the time, and 5=None of the time.
 
A higher SF scale score indicates better social functioning.

SF-36 RE scale score	
raw score = sum (items 5A, 5B, and 5C )  <math>RE = [(raw\ score - 3) / 12] * 100</math>  <math>RE\_Z = (RE - 87.50009) / 22.01216</math>  RE scale score = (RE_Z * 10) + 50
 
When calculating the raw score, if 2 or more of the items are non-missing then replace any missing values as follows:
 
Calculate the mean of the answered questions, using the number of answered questions as the denominator. Substitute the mean for any missing scores.
 
Otherwise, if less than 2 of the items are non-missing then RE scale score is missing.
 
Responses to the items in Question 5 range from 1 to 5 where 1=All of the time, 2=Most of the time, 3=Some of the time, 4=A little of the time, and 5=None of the time.
 
A higher RE scale score indicates better role-emotional functioning.

SF-36 MH scale score	
raw score = sum (items 9B, 9C, reversed 9D, 9F and reversed 9H)  <math>MH = (raw\ score - 5) * 5</math>  <math>MH\_Z = (MH - 75.76034) / 18.04746</math>  MH scale score = (MH_Z * 10) + 50
 
Reverse direction of scores for 9D and 9H, by subtracting score from 6.
 
If 3 or more of the items are non-missing then replace any missing values as follows:
 
Calculate the mean of the answered questions, using the number of answered questions as the denominator. Substitute the mean for any missing scores.
 
Otherwise, if less than 3 of the items are non-missing then MH scale score is missing.
 
The scale for these items ranges from 1 to 5 where 1=All of the time, 2=Most of the time, 3=Some of the time, 4=A little of the time, and 5=None of the time.
 
A higher MH scale score indicates better mental health.

SF-36 PCS score	
PCS score includes the 8 scales for GH, PF, RP, RE, SF, MH, BP, and VT.
 
<math>PF1 = (PF - 82.62455) / 24.43176</math>; <math>RP1 = (RP - 82.65109) / 26.19282</math>;  <math>BP1 = (BP - 73.86999) / 24.00884</math>; <math>GH1 = (GH - 70.78372) / 21.28902</math>;  <math>VT1 = (VT - 58.41968) / 20.87823</math>; <math>SF1 = (SF - 85.11568) / 23.24464</math>;  <math>RE1 = (RE - 87.50009) / 22.01216</math>; <math>MH1 = (MH - 75.76034) / 18.04746</math>;
 
Raw Score = ((GH1*.24954)+(PF1*.42402)+(RP1*.35119)+  (RE1*-.19206)+(SF1*-.00753)+(MH1*-.22069)+(BP1*.31754)+  (VT1*.02877))
 
PCS Summary Scale Score = (raw score *10) + 50
 
Raw Score is missing if one of the component scale scores is missing.

SF-36 MCS score	
MCS score includes the 8 scales for GH, PF, RP, RE, SF, MH, BP, and VT.
 
PF1=(PF-82.62455)/24.43176; RP1=(RP-82.65109)/26.19282;          BP1=(BP-73.86999)/24.00884; GH1 = (GH-70.78372)/21.28902;          VT1=(VT-58.41968)/20.87823; SF1=(SF-85.11568)/23.24464;          RE1=(RE-87.50009)/22.01216; MH1=(MH-75.76034)/18.04746;
 
Raw Score =((GH1*-.01571)+(PF1*-.22999)+(RP1*-.12329)+          (RE1*.43407)+(SF1*.26876)+(MH1*.48581)+(BP1*-.09731)+          (VT1*.23534))
 
MCS Summary Concept Score = (raw score *10) + 50
 
Raw Score is missing if one of the component scale scores is missing.

-----------------	--

